8.3 Response Duration

Response duration will be measured from the time measurement criteria for CR/PR (whichever is first recorded) are first met until the first date that recurrent or progressive disease is objectively documented, taking as reference the smallest measurements recorded on study (including baseline).

8.4 Stable Disease Duration

Stable disease duration will be measured from randomization until the criteria for progression are met, taking as reference the smallest sum on study (including baseline).

8.5 Methods of Measurement

The same method of assessment and the same technique should be used to characterize each identified and reported lesion at baseline and during follow-up. Assessments should be identified on a calendar schedule and should not be affected by delays in therapy. While on study, all lesions recorded at baseline should have their actual measurements recorded at each subsequent evaluation, even when very small (e.g. 2 mm). If it is the opinion of the radiologist that the lesion has likely disappeared, the measurement should be recorded as 0 mm. If the lesion is believed to be present and is faintly seen but too small to measure, a default value of 5 mm should be assigned. For lesions which fragment/split add together the longest diameters of the fragmented portions; for lesions which coalesce, measure the maximal longest diameter for the “merged lesion”.

8.5.1 Clinical Lesions

Clinical lesions will only be considered measurable when they are superficial and ≥ 10 mm as assessed using callipers (e.g. skin nodules). For the case of skin lesions, documentation by colour photography including a ruler to estimate the size of the lesion is recommended. If feasible, imaging is preferred.

8.5.2 Chest X-ray

Chest CT is preferred over chest X-ray, particularly when progression is an important endpoint, since CT is more sensitive than X-ray, particularly in identifying new lesions. However, lesions ≥ 20 mm on chest X-ray may be considered measurable if they are clearly defined and surrounded by aerated lung.

8.5.3 CT, MRI

CT is the best currently available and reproducible method to measure lesions selected for response assessment. This guideline has defined measurability of lesions on CT scan based on the assumption that CT slice thickness is 5 mm or less. When CT scans have slice thickness greater than 5 mm, the minimum size for a measurable lesion should be twice the slice thickness. MRI is also acceptable in certain situations (e.g. for body scans). Other specialized imaging or other techniques may also be appropriate for individual case [Eisenhauer 2009]. For example, while PET scans are not considered adequate to measure lesions, PET-CT scans may be used providing that the measures are obtained from the CT scan and the CT scan is of identical diagnostic quality to a diagnostic CT (with IV and oral contrast).

8.5.4 Ultrasound

Ultrasound is not useful in assessment of lesion size and should not be used as a method of measurement. If new lesions are identified by ultrasound in the course of the study, confirmation by CT is advised.

8.5.5 Endoscopy, Laparoscopy

The utilization of these techniques for objective tumour evaluation is not advised. However, they can be useful to confirm complete pathological response when biopsies are obtained or to determine relapse in trials where recurrence following complete response or surgical resection is an endpoint.

8.5.6 Tumour Markers

Tumour markers alone cannot be used to assess objective tumour response. If markers are initially above the upper normal limit, however, they must normalize for a patient to be considered in complete response.

8.5.7 Cytology, Histology

These techniques can be used to differentiate between PR and CR in rare cases if required by protocol (for example, residual lesions in tumour types such as germ cell tumours, where known residual benign tumours can remain). When effusions are known to be a potential adverse effect of treatment (e.g. with certain taxane compounds or angiogenesis inhibitors), the cytological confirmation of the neoplastic origin of any effusion that appears or worsens during treatment when the measurable tumour has met criteria for response or stable disease is advised to differentiate between response or stable disease and progressive disease.

9.0 SERIOUS ADVERSE EVENT REPORTING

The descriptions and grading scales found in the NCI Common Terminology Criteria for Adverse Events (CTCAE) will be utilized for Adverse Event (AE) reporting (version can be found in Appendix V). All appropriate treatment areas should have access to a copy of the CTCAE. A copy of the CTCAE can be downloaded from the CTEP web site: (http://ctep.cancer.gov/protocolDevelopment/electronic_applications/ctc.htm).

All serious adverse events (SAE) defined as per ICH guidelines (see below) and other adverse events must be recorded on case report forms. In addition, all “reportable” serious adverse events are subject to expedited reporting using the CCTG SAE form. The term ‘reportable SAE’ is used in the definitions which follow to describe those SAEs which are subject to expedited reporting to CCTG.

9.1 Definition of a Reportable Serious Adverse Event (Durvalumab +/- Tremelimumab Arm)

- For patients randomized to receive best supportive care (BSC), SAE reporting is NOT required.
- All serious adverse events, regardless of whether they are unexpected or related to protocol treatment, occurring during the treatment period and within 30 days after the last protocol treatment administration, must be reported in an expedited manner. Any late serious adverse event occurring after this 30-day period which is related to protocol treatment must also be reported in an expedited manner (see Section 9.2 for reporting instructions).
- A serious adverse event (SAE) is any adverse event that at any dose:
 - results in death
 - is life-threatening
 - requires inpatient hospitalization or prolongation of existing hospitalization (excluding hospital admissions for study drug administration, transfusional support, scheduled elective surgery and admissions for palliative or terminal care)
 - results in persistent or significant disability or incapacity
 - is a congenital anomaly/birth defect

Medical and scientific judgement should be exercised in deciding whether expedited reporting is appropriate in other situations such as important medical events that may not be immediately life-threatening or result in death or hospitalization but may jeopardize the patient or may require intervention to prevent one of the events listed above.

Important Notes:

1. Any immune-related adverse event (irAE) requiring high dose steroids is by definition medically significant and must be reported as such (i.e., as expedited events using the SAE reporting system).
2. If a patient shows an AST or ALT ≥ 3 x ULN together with total bilirubin ≥ 2 x ULN, refer to Appendix III for further instructions on cases of increases in liver biochemistry and evaluation of Hy’s Law. These cases should be reported as SAEs if, after evaluation, they meet the criteria for a Hy’s law case or if any of the individual liver test parameters fulfill any of the SAE criteria.

9.1.1 Durvalumab +/- Tremelimumab Adverse Events of Special Interest

An adverse event of special interest (AESI) is one of scientific and medical interest specific to understanding of the Investigational Product and may require close monitoring. An AESI may be serious or non-serious.

AESIs for durvalumab ± tremelimumab include, but are not limited to events with a potential inflammatory or immune-mediated mechanism and which may require more frequent monitoring and/or interventions such as steroids, immunosuppressants and/or hormone replacement therapy. **These AESIs may require close monitoring in the treatment arms with durvalumab ± tremelimumab.**

An immune-mediated adverse event (imAE) is defined as an AESI that is associated with drug exposure and is consistent with an immune-mediated mechanism of action and where there is no clear alternate etiology. Serologic, immunologic, and histologic (biopsy) data, as appropriate, should be used to support an imAE diagnosis. Appropriate efforts should be made to rule out neoplastic, infectious, metabolic, toxin, or other etiologic causes of the imAE.

If the Investigator has any questions in regards to an event being an imAE, the Investigator should promptly contact the CCTG.

AESIs observed with durvalumab ± tremelimumab include:

- Diarrhea / Colitis, and intestinal perforation;
- Pneumonitis / Interstitial Lung Disease (ILD);
- ALT/AST increases / hepatitis / hepatotoxicity;
- Neuropathy / neuromuscular toxicities (e.g. Guillain-Barré syndrome, and myasthenia gravis);
- Endocrinopathies (i.e. events of hypophysitis, hypopituitarism, adrenal insufficiency, diabetes insipidus, hyper- and hypothyroidism and type I diabetes mellitus);
- Rash / Dermatitis;
- Nephritis / Blood creatinine increases;
- Pancreatitis (or labs suggestive of pancreatitis - increased serum lipase , increased serum amylase);
- Myocarditis;
- Myositis/polymyositis
- Other inflammatory responses that are rare with a potential immune-mediated aetiology include, but are not limited to, pericarditis, sarcoidosis, uveitis and other events involving the eye, skin, hematological and rheumatological events.

In addition, infusion-related reactions and hypersensitivity/anaphylactic reactions with a different underlying pharmacological etiology are also considered AESIs.

Further information on these risks (e.g. presenting symptoms) can be found in the current version of the durvalumab and tremelimumab Investigator's Brochures. More specific guidelines for their evaluation and treatment are described in detail in Appendix III.

9.1.2 Events **Not** to be Treated as SAEs (Durvalumab +/- Tremelimumab Arm)

- Serious adverse events which are unequivocally related to the underlying malignancy or disease progression do **NOT** require expedited reporting. These include such adverse events as admission for pain control, palliative care or paracentesis of malignant effusions.
- In addition, the following events will **NOT** be recorded as AEs (or SAEs):
 - lack of efficacy /disease progression (will be recorded separately on CRF);
 - laboratory abnormalities for protocol specified tests (these are derived electronically from actual values supplied and need not be reported separately in adverse event tables on CRFs);
 - elective hospitalization for medical, radiological or surgical procedures for treatment of disease or to simplify treatment for study procedures (will be recorded separately on CRF);
 - hospitalization for palliative care or pain control.

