5.1 Patient Evaluation Flowsheet: Pre-study (Baseline) and Post-randomization Follow-up
For Patients Randomized to Best Supportive Care (Arm 1)

| Required Investigations | PRE-STUDY (≤ 14 days prior to randomization, unless otherwise indicated) | PRIOR to objective disease progression (timing from randomization) | | AFTER objective disease progression (timing from randomization) |
|---|---|---|--|--|
| | | Every 4 weeks until objective disease progression | Every 8 weeks until objective disease progression (maintain schedule even if clinic visits are delayed) ³ | Every 12 weeks |
| History and Physical Exam | | | | |
| Including: height (baseline only), weight, ECOG performance status, clinical tumour measurements (if applicable) | X | X | | |
| Vital Signs (blood pressure, heart rate, temperature) | X | X | | |
| Concomitant Medications | X | X | | |
| Overall Survival | | | | |
| Survival Status Assessment | | X | X | X ¹ |
| Hematology | | | | |
| CBC, differential (including lymphocytes), platelets | X | X | | |
| Coagulation | | | | |
| PTT, PT/INR | X | X | | |
| Biochemistry | | | | |
| Serum Creatinine, Chloride, Sodium, Potassium, Calcium, Magnesium, Bilirubin, ALP, AST and ALT, LDH, Albumin, TSH ² , Amylase, Lipase, Serum CEA | X | X | | |
| Creatinine Clearance (calculated) | X | as clinically indicated | | |
| Glucose | X | as clinically indicated | | |
| Radiology³ | | | | |
| Chest/abdomen/pelvis CT or MRI scan ³ | X ≤ 28 days | | X ³ | |
| Other scans as necessary to document all measurable and non-measurable disease ³ | X ≤ 28 days | | | |
| Other Investigations | | | | |
| Pregnancy Test ⁴ | X | | | |
| ECG | X | as clinically indicated | | |
| Dipstick Urinalysis (including protein, specific gravity, glucose and blood) | X | | | |

table continued on next page ...

| Correlative Studies | | | |
|--|--|---|--|
| Archival Tissue Sample ⁵ (mandatory) | Availability of sufficient tissue must be confirmed prior to randomization | Submit tissue within 4 weeks of randomization | |
| Whole blood, plasma and serum ^{5,6} (mandatory) | X | To be done at 8 weeks, and at the time of objective disease progression ⁷ , if not already done | |
| Adverse Events | | | |
| Adverse Event Assessment ⁸ | X (To document residual adverse events from previous therapy and baseline symptoms) | X To be evaluated continuously for adverse events (until objective disease progression) | |
| Quality of Life | | | |

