| 
 All patients will be seen at 4 weeks after the end of the last cycle date. Thereafter, continued follow-up is not required for patients who go off protocol treatment with unequivocal progressive disease, except to document ongoing toxicities (until resolved to < grade 2) and late toxicities (including second malignancies). For patients who go off protocol treatment with CR, PR, or SD ongoing, follow-up will be required every 12 weeks until relapse (see Appendix I for investigations to be performed). Death Report will be required for all patients. Due within 2 weeks of knowledge of death (see Appendix IV - Documentation for Study). Timing of Day 1 Assessments: Pre-treatment blood draws and physical exams may be done one working day prior to treatment if necessary, and when treatment is to begin on a Monday, may be done on the previous Friday (maximum 72 hours prior to treatment). In order to ensure that nadir counts are not missed, every effort should be made to do interim blood draws within 24 hours of the day specified in the protocol. If a patient shows an AST or ALT ≥ 3 x ULN together with total bilirubin ≥ 2 x ULN, refer to Appendix III for further instructions on cases of increases in liver biochemistry and evaluation of Hy's Law. These cases should be reported as SAEs if, after evaluation, they meet the criteria for a Hy's law case or if any of the individual liver test parameters fulfill any of the SAE criteria. Note: Labs do not need to be repeated Day 1, Cycle 1. In order to ensure that nadir counts are not missed, every effort should be made to do interim blood draws within 24 hours prior to the day specified in the protocol. Vital signs are to be monitored before, during, and after the infusion of tremelimumab and durvalumab with assessment of vital signs to be collected ≤ 30 minutes prior to start of infusion then every 30 ± 5 minutes during infusion and observation periods. A 1-hour observation period is recommended after the first infusion of tremelimumab, during which time durvalumab may be administered (see Section 7.1.3). A second 1-hour observation period is recommended after the first infusion of durvalumab. If no clinically significant infusion reactions are observed during or after the first cycle of tremelimumab and durvalumab, subsequent infusion observation periods can be at the Investigator's discretion but are recommended to be of 30 minutes, i.e., 30 minutes after tremelimumab infusion, during durvalumab infusion, and for 30 minutes after durvalumab infusion. For patients who receive only durvalumab, the recommended observation period is 30 minutes after infusion. In the event that patient is unable to attend clinic, post-progression follow-up may be by means of telephone contact. Hematology, Coagulation and Biochemistry investigation to be done after objective progression ONLY if there are ongoing hematologic AEs that are related to protocol treatment. If abnormal, T3 and T4 must be measured. To ensure comparability, scans must identify and report each lesion at baseline and at reassessment during treatment. These scans must be performed using identical technique (i.e. scans performed immediately following bolus contrast administration using a standard volume of contrast, the identical contrast agent, and preferably the same scanner). Tumour evaluations must be consistently performed every 8 weeks (i.e. at 8 weeks, 16 weeks, 24 weeks, 32 weeks etc. from randomization) until objective disease progression is documented (as described in Section 8). Sites should adhere to this calendar-based schedule regardless of any delays in treatment. If a radiology scan is done off schedule, future protocol-required scans should still be performed based on the original schedule, i.e. every 8 weeks counting from randomization (not from the date of the off schedule scan). For women of childbearing potential only. May be urine or serum. Pregnancy test (in women of childbearing potential), as part of Pre-Study Evaluation, may include an ultrasound to rule-out pregnancy. See Section 12.0 and the CO.26 Correlative Studies Laboratory Manual for details. Whole blood, plasma and serum should be obtained as close to the time of objective progression as possible and should be done within 28 days (e.g. at the next clinic visit). Blood for correlatives done within 28 days PRIOR to date of progression does not need to be repeated. Adverse Events to be evaluated using the NCI Common Terminology Criteria for Adverse Events (CTCAE v4.0) (see Appendix V). See Section 7 and Appendix III for additional monitoring of patients with toxicity. Follow every adverse event felt related to study therapy until resolved to ≤ grade 2 – i.e. follow-up every 12 weeks until deterioration to ECOG PS 4 and/or end of life care or until all toxicities thought to be possibly-, probably-, or definitely-related to durvalumab or tremelimumab have resolved, returned to baseline, or been deemed irreversible, whichever is longer. To be completed by patient in clinic. | | | | | | |

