7.7.1 Adverse Events

Adverse events will be recorded on the CCTG toxicity/adverse event-intercurrent illness case report form. Events reported on Treatment Report or 4-Week Post-Treatment Follow-Up Report for patients on the Durva+Treme arm will be defined as adverse events on Durva+Treme; Events reported on any case report forms except Form 1 will be summarized separately for patients on both arms as overall adverse events during the (whole) study.

Drug related adverse events are those events with a relation to protocol therapy of 3=possible, 4=probable or 5=definite.

Severe adverse events are those events reported with a CTCAE Grade of 3 or higher.

Comparisons between treatment arms on overall adverse events (any vs. other, severe vs. other) will be carried out using a two sided Fisher's exact test at an alpha level of two-sided 10%.

The following variables are summarized. Tabulations of overall adverse events will be presented by treatment group.

- Adverse events on Durva+Treme: worst CTCAE grade per patient (**Table 42**)
- Severe adverse events on Durva+Treme: worst CTCAE grade per patient (**Table 43**)
- Drug related adverse events on Durva+Treme: worst CTCAE grade per patient (**Table 44**)
- Overall adverse events: worst CTCAE grade per patient (**Table 45**)
- Severe overall adverse events: worst CTCAE grade per patient (**Table 46**)

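### The list of events not recorded as adverse events is written for the drug arm only, so the planned between-arm AE test has no single event definition; the size and net direction of any bias are unknown

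*Protocol*

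**What the plan says.** - **Recording duty.** Protocol 9.0 says that SAEs "and other adverse events must be recorded on case report forms". It names no arm.
- **BSC exemption.** Protocol 9.1 states: "For patients randomized to receive best supportive care (BSC), SAE reporting is NOT required". This concerns SAE reporting and does not mention the AE form.
- **Exclusions.** The heading of Protocol 9.1.2 includes "to be Treated as SAEs (Durvalumab +/- Tremelimumab Arm". Its first bullet waives expedited reporting of SAEs clearly due to the malignancy, and gives pain-control and palliative admissions as examples of such adverse events. Its second bullet goes further and lists events that are not recorded as AEs or SAEs at all: "lack of efficacy /disease progression (will be recorded separately on CRF"), laboratory abnormalities on protocol-specified tests, elective hospitalization, and "hospitalization for palliative care or pain control".
- **AE windows.** The BSC flowsheet (Protocol 5.1) reads "To be evaluated continuously for adverse events (until objective disease progression") and carries no exclusion list. The Arm 2 flowsheet (Protocol 5.2) covers the treatment period and a visit 4 weeks after the end of the last cycle. A footnote then adds "Follow every adverse event felt related to study therapy until resolved to" a stated grade, and this continues after progression.
- **Analysis.** SAP 7.7.1 says: "Comparisons between treatment arms on overall adverse events (any vs. other, severe vs. other) will be carried out" by a two-sided Fisher's exact test at 10%. Overall AEs come from every case report form except Form 1, in both arms (Tables 45 and 46).

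**The concern.** A between-arm test of AE proportions needs the same definition of an event in both arms. Here the only text that removes progression and palliative or pain admissions from AE recording is addressed to Arm 2. A BSC site that follows the protocol literally has a general duty to record AEs, an exemption from SAE reporting only, and no instruction to leave these events off the AE form.

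Toxicity and safety is a secondary objective (Protocol 1.2), and Protocol 13.1 names a comparison of AEs between arms. The trial is open-label (SAP 2.1) and the population has refractory disease, so disease-related admissions can be expected in both arms. If they enter one count and not the other, part of the difference in Tables 45 and 46 reflects recording rules and not treatment.

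**Working it through.** **1. The texts side by side**

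| Question | Arm 2 | BSC |
|---|---|---|
| Are AEs recorded on case report forms? | Yes (9.0) | Yes (9.0) |
| Is SAE reporting required? | Yes (9.1) | No (9.1) |
| Are progression and palliative or pain admissions kept off the AE form? | Yes (9.1.2, second bullet) | Not stated |
| When does AE assessment end? | At least 4 weeks after the last cycle; later for related events (5.2) | At objective progression (5.1) |
| Is the arm in the Fisher test? | Yes (SAP 7.7.1) | Yes (SAP 7.7.1) |

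The third row is the gap. The fourth is a separate asymmetry that bears on direction.

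**2. The plan's own figures.** Neither document states an AE rate or a power for the AE comparison, so there is no figure to reproduce on this point. The planned arm sizes, 120 and 60, come from SAP 2.1. All AE rates below are assumptions.

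**3. Illustration of the recording gap alone.** Let p2 and p1 be the AE proportions on Arm 2 and BSC under a common rule. Let x be the share of otherwise AE-free BSC patients who are counted only through an event that 9.1.2 excludes on Arm 2. The recorded BSC proportion is then

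q = p1 + (1 − p1)·x.

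For example, p1 = 0.30 and x = 0.10 give 0.30 + 0.70 × 0.10 = 0.37. Exact enumeration of the two-sided 10% Fisher test with 120 against 60 patients gives the chance of a significant result with more AEs on Arm 2:

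| p2 vs p1 (assumed) | x = 0 | x = 5% | x = 10% | x = 20% |
|---|---|---|---|---|
| 50% vs 30% | 80% | 64% | 46% | 16% |
| 60% vs 40% | 79% | 66% | 52% | 23% |
| 40% vs 20% | 85% | 66% | 44% | 11% |

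With no true difference (30% in both arms), the chance of a significant result with more AEs on BSC rises from 4.5% at x = 0 to 23% at x = 10%. A common rule sets x to 0.

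**4. The window difference pushes the other way.** Assume the same background AE rate λ in both arms, a BSC window of 8 weeks (8 × 7/30.4375 = 1.84 months), and 4 or 8 further weeks on Arm 2 (0.92 or 1.84 months). The recorded proportion is 1 − exp(−λ × window). The x that would cancel the gap is 1 − exp(−λ × extra time).

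| λ per month | Extra time | BSC | Arm 2 | Chance of a false excess on Arm 2 | x needed to cancel |
|---|---|---|---|---|---|
| 0.1 | 4 weeks | 17% | 24% | 27% | 9% |
| 0.1 | 8 weeks | 17% | 31% | 64% | 17% |
| 0.2 | 4 weeks | 31% | 42% | 40% | 17% |
| 0.2 | 8 weeks | 31% | 52% | 84% | 31% |

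The two mechanisms oppose each other, and the documents fix the size of neither.

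**The case against.** The arm label has a likely innocent origin. Protocol 9.1 carries the same label because only Arm 2 has SAE reporting, and a section on exceptions to SAE reporting would naturally inherit it. Nothing tells BSC sites to enter progression or palliative admissions as AEs. The Relapse/Progression Report and the Death Report apply to both arms, although other forms in Appendix IV are marked for one arm. Laboratory abnormalities are on the same list, yet SAP 7.7.2 derives them from reported values in both arms. Protocol 13.2 plans the Fisher test only if required.

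Much of this stands as evidence of intent, but it does not close the gap. Inheritance from SAE reporting explains the first bullet of 9.1.2, not the second, which governs AE recording. The first bullet itself calls pain and palliative admissions adverse events, so without an exclusion the duty in 9.0 reaches them. The Relapse/Progression Report is triggered by objective progression, and Protocol 8.2.6 says that symptomatic deterioration is not objective progression. Decline before a confirming scan can therefore fall inside the BSC AE window. SAP 7.7.1 plans the test without the condition in Protocol 13.2.

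A reader might infer that the gap hides drug toxicity. The documents do not support that. The AE windows act in the opposite direction, and Tables 42 to 44, 57 and 58 report Arm 2 toxicity without reference to BSC. A reader might also infer that a colorectal cancer death counts as an AE on BSC only. Death is not on the not-recorded list, so early mortality cannot be used to size the effect. The list removes the admission, not the symptom behind it. Severe pain remains gradable in both arms, and the extra BSC patients could be few or none.

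**Conclusion.** The point holds as a defect of specification. Followed literally, the plan tests AE proportions between arms under a recording rule written for one of them. Taken alone, the gap can add disease-related events only to the BSC count. Its size is unknown: the tabulated losses of power rest on assumed AE rates and assumed values of x, and they show sensitivity, not an estimate. The net direction of bias in the Fisher tests cannot be determined, because the longer AE window on Arm 2 works against the gap. How sites actually recorded these events on BSC is not in the documents. The primary overall survival analysis is unaffected.

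**What to change.** - **Protocol Section 9.** Move the not-recorded list from the second bullet of 9.1.2 to 9.0, as one AE-recording rule for both arms. Leave only the expedited-reporting text specific to Arm 2. At the same time, reconcile the two bullets: one treats a pain or palliative admission as an SAE exempt from expedited reporting, the other as neither an AE nor an SAE.
- **SAP 7.7.1.** State that the same listed exclusions are applied to both arms before Tables 45 and 46 and the Fisher tests. SAP 2.1 records that randomization closed in June 2017, so this sentence is what deals with entries already made.
- **Deaths.** Do not add death from colorectal cancer as an exclusion unless it is applied identically in both arms, using the cause on the Death Report.

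The cost is a change of heading and placement and one sentence in the SAP. Some BSC entries may need recoding at analysis. SAP 7.7.1 describes only relation to protocol therapy for AEs, so that recoding may need a review of event terms. The change does not remove the difference in AE windows, which should be stated beside the test results.
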